7.1 General Treatment Information

a. Concomitant Medications

Concomitant medications must be assessed prior to initiation of antiviral therapy in Arm 1 (prophylaxis) or if initiated if HBV reactivation occurs (upon indication) in Arms 2 and 3.

Refer to the current FDA-approved package insert for the most comprehensive and up to date information on concomitant medications.

TAF: Concomitant administration of oxcarbazepine, phenobarbital, phenytoin, rifabutin, rifampin, rifapentine, or St. John's Wort is not recommended. If co-administered with carbamazepine, TAF dose should be increased to two tablets once daily. Alternatively, if the above medications cannot be stopped, then study patients may take TDF or ETV.

TDF: none

ETV: none

If possible, avoid use of warfarin. If medically necessary, warfarin may be used during protocol participation after enrollment. For patients who need to take warfarin, monitor INR per [Section 9](#). If the patient has an INR increase, the treating investigator should review to determine if the cause is due to warfarin, study treatment, or acute liver injury. If INR increase is due to acute liver injury, and the increased INR is accompanied by AST, ALT, and bilirubin increase, evaluate the cause per [Section 9](#). Document this determination in the patient's chart.

b. Guidance for Offsite and Virtual Options during the Conduct of the Trial

1. **Laboratory assessments and specimen collections**: All laboratory assessments and specimen collections must be completed at protocol-specified timepoints (see [Section 9.0](#)).
2. **Conducting labs at an offsite facility**: In order to provide participating sites flexibility in treating patients, it is the intent of the **S1614** protocol to

allow for laboratory assessments to be drawn and resulted by local healthcare providers (with appropriate oversight by the Responsible Investigator [local treating investigator]), where administration of the assessment at an off-site facility is in the best interest of the patient and provides for continuity of patient care. Utilization of offsite / local healthcare resources for conduct of patient's laboratory assessments must be documented including procedures for oversight (by the Responsible Investigator) of assessments performed offsite.

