7.4 HBV Monitoring and Adverse Liver Outcomes

During anti-cancer therapy and for 24 months from initial registration, all patients will undergo monitoring for HBV reactivation and adverse liver outcomes (see [Section 10.0](#)). Patients will have ALT and total bilirubin assessed every 4 weeks (\pm 2 weeks) for the first 24 weeks, then every 8 weeks thereafter. Per usual care, if total bilirubin > 3 mg/dL or if ALT > 5x IULN or > 200 U/L then INR will be assessed.

As part of adverse liver outcome assessment, if a hepatitis flare occurs (defined as ALT > 3 x baseline and > 100 U/L) the following labs should be ordered on the same day as the flare or within 7 days of the flare:

- direct bilirubin,
- HBV DNA,
- IgM anti-HAV, and
- either anti-HCV or HCV RNA.

- Patients on Arms 1, and 2 must have HBeAg tested. HBV test results must be reported on the **S1614** Laboratory Values Form.
- If Patients on Arms 3 and 4 become HBsAg positive and have a hepatitis flare, HBeAg testing is required. HBV test results must be reported on the **S1614** Laboratory Values Form.

Additionally, for all HBsAg+ patients, it is recommended that the treating investigator contact [name], M.D., [name], M.D., or [name] at [contact] for evaluation during the study treatment and after discontinuation of study treatment to ensure continued monitoring and to determine whether antiviral therapy should be maintained after discontinuation of study treatment.

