9.0 STUDY CALENDAR

9.1 ARM 1: Prophylactic anti-HBV therapy Arm (HBsAg+ Patients)

REQUIRED STUDIES	Week 0 (Registration)	Weeks from Registration (± 2 weeks unless otherwise specified)							Follow-Up after Off HBV Treatment (Every 8 Weeks Through Week 104) Every 8 Weeks from Week 32 through Week 104 (24 months)	at HBV Reactivation	
		4	8	12	16	20	24				
PHYSICAL											
History and Physical Exam	X										
HBV Assessment ^(F)	X	X	X	X	X	X	X	X	X	X	
Toxicity Notation ^(F)		X	X	X	X	X	X	X			
Review Intake Calendar ^(F)		X	X	X	X	X	X	X			
LABORATORY											
Serum creatinine/Creatinine Clearance	X	X	X	X	X	X	X	X			
Total Bilirubin	X	X	X	X	X	X	X	X	X		
Direct Bilirubin ^{(A) (E)}	X	X	X	X	X	X	X	X	X		
ALT	X	X	X	X	X	X	X	X	X		
International Normalized Ratio (INR) ^(A)	X	X	X	X	X	X	X	X	X		
Complete Blood Count (CBC)	X										
HBV DNA ^(B)	X	X	X	X	X	X	X	X	X		
IgM anti-HAV ^{(B) (E)}	X	X	X	X	X	X	X	X	X		
anti-HCV ^{(B) (E)} or HCV RNA ^{(B) (E)}		X	X	X	X	X	X	X	X		
HBeAg ^(B)	X	X	X	X	X	X	X	X	X		

Calendar 9.1 continued on next page. Click here for [Footnotes](#)

REQUIRED STUDIES	Week 0 (Registration)	Weeks from Registration (± 2 weeks unless otherwise specified)							Follow-Up after Off HBV Treatment (Every 8 Weeks Through Week 104) (24 months)	at HBV Reactivation
		4	8	12	16	20	24			
SPECIMEN SUBMISSION ^(C)										
Serum (10 ml blood in red top tube)	X		X		X		X	X		X
Whole blood (50 ml in EDTA tubes)	X			X			X			X
TREATMENT										
Arm 1- Prophylactic Anti-HBV Therapy ^(D)	X	X	X	X	X	X	X	X		

NOTE: Forms are found on the protocol abstract page on the SWOG website (www.swog.org). Forms submission guidelines are found in [Section 14.0](#). Click here for [Footnotes](#).

NOTE: Unless indicated otherwise in the protocol, scheduled procedures and assessments (treatment administration, toxicity assessment for continuous treatment, disease assessment, specimen collection and follow-up activities) must follow the established SWOG guidelines as outlined in SWOG Best Practices, <https://www.swog.org/clinical-trials/protocol-workbench>.

FOOTNOTES:

- (A) If total bilirubin > 3 mg/dL, or if ALT > 5 x IULN or > 200 U/L, per usual care (see [Section 7.4](#)).
- (B) If hepatitis flare (defined as ALT > 3 x baseline and > 100 U/L).
- (C) See [Sections 15.0](#) and [Appendix 18.1](#).
- (D) See [Section 7.2a](#).
- (E) To be ordered the same day (or within 7 days) if hepatitis flare occurs.
- (F) See [Section 7.1b](#).

Allowable Windows

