10.0 CRITERIA FOR EVALUATION AND ENDPOINT ANALYSIS

10.1 Primary Endpoint

a. Adverse liver outcome: Defined as liver-related death or liver failure (ascites, hepatic encephalopathy or impaired hepatic synthetic function defined as total bilirubin ≥ 5 mg/dL or INR ≥ 2.0) not due to disease progression in the liver. Assessment of the primary endpoint will be made by sites and subsequently adjudicated by the research oversight team by blinded review (see [Appendix 18.4](#)).

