18.1 Translational Medicine

HBV DNA, HBsAg, ultrasensitive HBsAg, anti-HBs, HBV RNA, HBV core-related antigen (HBcrAg)

Blood specimens for 444 study participants enrolled in the main clinical study will be collected at baseline and at regular intervals after registration as outlined above in [Section 9.0](#) Study Calendar and [Section 15.0](#). Sixty sites will enroll 222 chronic HBV and 222 past HBV patients, collect blood specimens at study time points, and send specimens to the SWOG Biospecimen Bank. The SWOG Biospecimen Bank will prepare and batch-ship specimens to Toronto Centre for Liver Disease Laboratories during the main clinical study for research tests (HBV DNA, HBsAg, ultrasensitive HBsAg, HBV RNA, HBcAg, anti-HBs, and HBeAg tests) to retrospectively identify patients with HBV reactivation. The results from labs at Toronto Centre for Liver Disease will be used to determine cases of HBV reactivation and matched controls.

a. Specimen Collection and Processing:

Specimens for the TM studies will be collected in red top tubes at 5 time points (+/- 4 weeks) and processed at the site as detailed in [Section 15.0](#).

See Section 18.1d for SWOG Biospecimen Banking Instructions

At the end of the study, the bank will ship specimens to The Toronto Centre for Liver Disease labs where the following HBV tests will be performed: HBV DNA, HBsAg, ultrasensitive HBsAg, HBV RNA, HBcAg, anti-HBs, and HBeAg tests. ALT, total bilirubin, and INR will be performed as part of routine monitoring in the main clinical study SWOG [S1614](#).

b. **Translational Aim 1. To determine baseline and changes in overall immune status and HBV-specific immune response in solid tumor patients with chronic or past HBV infection receiving anti-cancer therapy, and to compare the differences in these immune responses by HBV reactivation status.**

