Serum analysis to identify serum biomarkers predicting HBV reactivation. We will use clinical assays to quantify HBV-specific antibodies in the serum and a comprehensive CBA or luminex assay to analyze immunological cytokines/chemokines in longitudinal serum samples. Arginase will be measured by ELISA. HBV RNA, HBcrAg and ultrasensitive HBsAg will be measured in the serum by qPCR (RNA) and ELISA (HBcrAg and ultrasensitive HBsAg) in patients who do and do not experience HBV reactivation to determine if the levels of these markers that indicated active transcription of HBV DNA in the liver increase prior to clinical reactivation and could be used as biomarkers of impending reactivation.

Understanding the serum profile of key molecules associated with HBV reactivation may provide a baseline predictor of HBV control during chemotherapy.

c. **Translational Aim 2. To identify demographic and clinical predictors and correlative immunologic biomarkers of HBV reactivation after receipt of anti-cancer therapy in patients with solid tumors and chronic or past HBV infection.**

The determinants of HBV reactivation in patients with solid tumors are not known. In this aim, we will identify the demographic and clinical predictors as well as immune correlates of HBV reactivation and hepatitis flare among all 444 study patients. For Aim 2, all immune studies will be performed on stored plasma and PBMCs that would have already been prospectively collected at predetermined time points as noted in [Section 9.0](#) Study Calendar and [Section 15.0](#) above. Immune tests will include ELISA, ICC assay, IFN-gamma elispot. If any immune test listed for Aim 2 has already been performed as part of the case control study in Aim 1, it will not be repeated in this aim. In the main clinical study, SWOG sites will collect clinical information for use in Aim 2. The following tests will be considered usual care monitoring for HBV patients receiving anti-cancer therapy and will be recorded at the study follow up time points listed in [Section 9.0](#) Study Calendar: ALT, total bilirubin, and INR. The primary outcome for Aim 2 is time to first evidence of HBV reactivation.

Statistical Analyses plan

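### INR of 2.0 or more is by itself a primary-endpoint event, but the protocol says both that post-baseline INR is drawn only after a bilirubin or ALT trigger and that it is routine, so endpoint ascertainment can differ between sites

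*Combined protocol and SAP*

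**What the plan says.** **Endpoint.** Section 10.1 defines one form of liver failure as "impaired hepatic synthetic function defined as total bilirubin ≥ 5 mg/dL or INR ≥ 2.0". The two laboratory criteria are joined by an or, so INR alone is enough.

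**Triggered INR.** Section 7.4 sets the scheduled tests: "Patients will have ALT and total bilirubin assessed every 4 weeks" for 24 weeks, then every 8 weeks. INR is not among them and is conditional: "if total bilirubin > 3 mg/dL or if ALT > 5x IULN or > 200 U/L then INR will be assessed". In calendars 9.1, 9.2 and 9.3 the INR row has X marks at the visits but carries footnote (A), which in 9.1 reads "If total bilirubin > 3 mg/dL, or if ALT > 5 x IULN or > 200 U/L, per usual care". The tests that Section 7.4 requires at a hepatitis flare (direct bilirubin, HBV DNA, hepatitis A and C tests, HBeAg where applicable) do not include INR.

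**Routine INR.** Appendix 18.1 states without condition that "ALT, total bilirubin, and INR will be performed as part of routine monitoring in the main clinical study". Under Translational Aim 2 it adds: "The following tests will be considered usual care monitoring for HBV patients receiving anti-cancer therapy and will be recorded at the study follow up". That sentence goes on to point to the Section 9 calendar and names INR beside ALT and total bilirubin.

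**Related text.** Section 5.3 requires INR at baseline for everyone. Section 7.1a says "For patients who need to take warfarin, monitor INR per" Section 9, where INR is conditional. Appendix 18.5 bases the blinded review on the chart information relevant to the primary endpoint.

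**The concern.** A component of the primary endpoint can be recorded only if the test is done. One site may read Section 7.4 and footnote (A) and draw INR on a trigger. Another may read Appendix 18.1, or the X marks, and draw it at every visit. Both would be following the protocol, yet they would apply different detection rules to the same endpoint.

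At a site that follows the trigger, an INR of 2.0 or more with bilirubin at or below 3 mg/dL and ALT below both cut-offs prompts no test. The event is then missed, or it is dated later, when a trigger is crossed at a subsequent visit. Central review cannot recover a value that was never measured.

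Two things are at stake: power, because few events are expected, and comparability of the arms, because the trigger uses ALT in part. Section 2.1 says that antiviral therapy can prevent reactivation and that reactivation can raise ALT, and Section 1.2 compares flare by arm. The number of INR tests could therefore differ between arms.

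**Working it through.** **1. What each text implies for a patient with INR of 2.0 or more, bilirubin at or below 3 mg/dL, and ALT below both cut-offs**

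| Text | Post-baseline INR drawn? |
|---|---|
| Section 7.4 | No |
| Calendars 9.1 to 9.3 | X at visits, but footnote (A) makes it conditional: no |
| Section 7.4 flare panel (ALT above 3 times baseline and above 100 U/L) | No, INR is not in the panel |
| Appendix 18.1, routine-monitoring sentence | Yes |
| Appendix 18.1, Aim 2 | Yes as worded, though it points to Section 9, where footnote (A) applies |
| Section 10.1 | If drawn, the value meets the laboratory criterion |

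**2. The plan's own power.** Inputs from Section 11.1: 100 per arm, 10% control event rate at 1 year, hazard ratio 0.30, death hazard 0.223, one-sided alpha 0.05, stated power 80%. Follow-up is 24 months (Section 7.8).

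- Event hazards: control −ln(0.90) = 0.1054; experimental 0.30 × 0.1054 = 0.0316.
- Expected events per arm = 100 × h/(h + 0.223) × [1 − exp(−2(h + 0.223))].
- Control 15.4, experimental 5.0, total 20.4.
- Freedman log-rank power = Φ(√d × (1 − HR)/(1 + HR) − 1.645) = Φ(4.517 × 0.538 − 1.645) = 78.4%.

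This is within 2 points of the stated 80%. As a check on method, assuming 2.5 years of uniform accrual plus 1 year of follow-up gives 21.6 events and 80.5%. The same set-up gives 91.8% and 96.6% for control rates of 15% and 20%, against the stated 92% and 97%. That variant follows early entrants beyond 24 months, so the 24-month figure is used below. Schoenfeld's formula gives 85.9% at 20.4 events and is not the better match.

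**3. Effect of losing events equally in both arms.** The share lost is an assumption; the hazard ratio stays at 0.30.

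| Share lost | Events | Power | Change from 78.4% |
|---|---|---|---|
| 5% | 19.4 | 76.6% | −1.8 points |
| 10% | 18.4 | 74.6% | −3.8 points |
| 20% | 16.3 | 70.2% | −8.2 points |
| 30% | 14.3 | 65.2% | −13.2 points |

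In the accrual variant, losses of 10% and 20% take 80.5% to 76.7% and 72.4%, nearly the same falls.

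**4. Burden if INR were scheduled.** Visits at weeks 4 to 24 (6) and weeks 32 to 104 (10) make 16. For 444 patients that is at most 16 × 444 = 7,104 tests, before deaths and dropout.

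**The case against.** The strongest reply is that triggered INR is a legitimate trade of sensitivity for specificity, and that little is lost. Bilirubin above 3 mg/dL opens the gate without any ALT rise, well below the endpoint cut-off of 5 mg/dL. Ascites, encephalopathy, bilirubin of 5 mg/dL or more and liver-related death need no INR. Nothing forbids an INR drawn for clinical reasons, and sites must submit source documents for any adverse liver outcome (Section 14.4f). Scheduled INR would also bring in warfarin-related values: Section 5.2h excludes warfarin at entry, but Section 7.1a allows it afterwards, and Section 10.1 has no exception for anticoagulation. All of this stands. It limits the likely loss and argues against presuming that scheduled INR is the answer. It does not reconcile Section 7.4 with Appendix 18.1.

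It can also be said that the Aim 2 sentence defers to Section 9 and so to footnote (A). That is a fair reading of that sentence, but the other sentence in Appendix 18.1 has no such pointer.

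A reader might go further and infer detection bias in favour of the experimental arm. The documents do not support that:

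- The visits and numeric trigger are the same for all patients.
- In Cohort 2 neither arm receives an antiviral by assignment at entry. Arm 3 starts on reactivation and Arm 4 at the physician's discretion.
- Section 3 lists raised ALT as an adverse effect of all three drugs, which could push testing the other way.
- No testing rate by arm, and no share of INR-only events, is given.

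**Conclusion.** The point holds as a conflict over how a primary-endpoint component is ascertained. Sections 7.4 and 9 make post-baseline INR conditional, Appendix 18.1 makes it routine, and Section 10.1 lets INR alone define an event. Events below the triggers can be missed or delayed. It would be too strong to say that they cannot be detected, or that detection rests on ALT alone.

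The size is conditional. With about 20 expected events per cohort, an equal loss of 10 to 20% costs about 4 to 8 points of power. That rests on the design's own rates, 24 months of follow-up, Freedman's formula and an assumed loss. It also supposes that the 10% control rate counts such INR events, which Section 11.1, calling that rate a best estimate, does not say.

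Testing frequency may differ by arm, most plausibly in Cohort 1, where Arm 1 receives an antiviral by assignment. The direction and magnitude of any resulting bias cannot be derived from the documents, so no figure is attached to it.

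**What to change.** Reconcile Section 7.4, the footnotes of calendars 9.1 to 9.3 and Appendix 18.1 into one INR ascertainment rule that applies to all arms. Either option resolves the conflict:

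- **Scheduled.** INR is drawn with each scheduled ALT and total bilirubin, as Appendix 18.1 states, and footnote (A) is removed from the INR rows. Cost: an added test at existing blood draws (up to about 7,100 in all), and adjudication of warfarin-related values, for which the blinded review would need a stated rule.
- **Triggered.** The trigger stays. Section 10.1 says that the INR component is assessed under it, Appendix 18.1 is corrected to match, and the meaning of the X marks is made plain. Cost: wording only, with the limited sensitivity acknowledged.

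Under either option, report the number of INR tests done by arm in each cohort beside the primary result. Add a sensitivity analysis of the primary endpoint that does not count events qualifying through INR alone; such patients stay at risk for the other components. Both use data already collected.

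Reconcile the cross-reference from Section 7.1a to Section 9 for patients on warfarin at the same time. The change should be made promptly, because tests not taken cannot be recovered later.

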7.5 Drug Compliance Documentation

Drug compliance will be recorded by patients in the Intake Calendar (see [Appendix 18.3](#)). Institutional CRAs will review and ascertain patient adherence with protocol therapy at the end of treatment. Calendar should be kept in the patient's research chart. Sites utilizing the CIRB must use the Intake Calendar provided. Sites not utilizing the CIRB may utilize institutional pill diaries or other source documentation in place of the Intake Calendar at the discretion of the treating physician.

7.6 Criteria for Removal from Protocol Treatment

- Completion of 24 months on study.
- If receiving anti-viral treatment, completion of anti-viral treatment 6 months after discontinuing all anti-cancer therapy or for up to 24 months after registration, whichever comes first.
- Cumulative delay of anti-viral treatment > 30 days for any reason.
- Unacceptable toxicity to anti-viral treatment. (See [Section 8.2](#))
- The patient may withdraw from the study at any time for any reason. If the patient allows for indirect follow-up or is refusing to complete any further patient forms but will allow the site to follow them indirectly, continue to submit the site-completed forms through Week 104.

7.7 Discontinuation of Treatment

All reasons for discontinuation of treatment must be documented in the Off Anti-Viral Protocol Treatment Notice.

7.8 Follow-Up Period

All patients will be followed until death or 24 months after registration, whichever occurs first. No further follow-up will be required once the patient completes 104 weeks (2 years) of protocol participation. Patients should continue to have their protocol-scheduled assessments until one of the outlined criteria for removal listed in [Section 7.6](#) has been met.

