9.2 ARM 2 & ARM 3: Upon Indication Arms (HBsAg+ or HBsAg- Patients)

REQUIRED STUDIES	Week 0 (Registration)	Weeks from Registration (± 2 weeks unless otherwise specified)						Follow-Up after Off HBV Treatment (Every 8 Weeks Through Week 104 (24 months)	at HBV Reactivation
		4	8	12	16	20	24		
PHYSICAL									
History and Physical Exam	X								
HBV Assessment ^(H)	X	X	X	X	X	X	X	X	X
Toxicity Notation ^{(G) (H)}		X	X	X	X	X	X	X	
Review Intake Calendar ^{(G) (H)}		X	X	X	X	X	X	X	
LABORATORY									
Serum creatinine/Creatinine Clearance	X	X	X	X	X	X	X	X	
Total Bilirubin	X	X	X	X	X	X	X	X	
Direct Bilirubin ^{(A) (F)}									
ALT	X	X	X	X	X	X	X	X	
International Normalized Ratio(INR) ^(A)	X	X	X	X	X	X	X	X	
Complete Blood Count	X								
HBV DNA ^{(B) (C) (F)}	X	X	X	X	X	X	X	X	
HBsAg ^(C)	Not Indicated in Arm 2*								
IgM anti-HAV ^{(B) (C) (F)}	X	X	X	X	X	X	X	X	
anti-HCV ^{(B) (C) (F)} or HCV RNA ^{(B) (C) (F)}		X	X	X	X	X	X	X	
Anti-HBs (Arm 3) ^{(B) (C) (F)}	X	X	X	X	X	X	X	X	
HBeAg (if become HBsAg+) ^{(B) (C) (F)}	X	X	X	X	X	X	X	X	

REQUIRED STUDIES	Week 0 (Registration)	Weeks from Registration (± 2 weeks unless otherwise specified)							Follow-Up after Off HBV Treatment (Every 8 Weeks Through Week 104 (24 months)	at HBV Reactivation
		4	8	12	16	20	24			
SPECIMEN SUBMISSION ^(D)										
Serum (10 ml blood in red top tube)	X		X		X		X	X		X
Whole blood (50 ml in EDTA tubes)	X			X			X			X
TREATMENT										
Upon-Indication anti-HBV therapy ^(E)	X	X	X	X	X	X	X	X		

NOTE: Forms are found on the protocol abstract page on the SWOG website (www.swog.org). Forms submission guidelines are found in [Section 14.0](#).

NOTE: Unless indicated otherwise in the protocol, scheduled procedures and assessments (treatment administration, toxicity assessment for continuous treatment, disease assessment, specimen collection and follow-up activities) must follow the established SWOG guidelines as outlined in SWOG Best Practices, <https://www.swog.org/clinical-trials/protocol-workbench>.

FOOTNOTES for Calendar 9.2:

- (A) If total bilirubin > 3 mg/dL, or if ALT > 5x IULN or > 200 U/L, per usual care (see [Section 7.4](#)).
- (B) If hepatitis flare (defined as ALT > 3 x baseline and > 100 U/L) if patient is HBsAg-positive.
- (C) If hepatitis flare (defined as ALT > 3 x baseline and > 100 U/L) in patient with baseline HBsAg-negative.
- (D) See [Sections 15.0](#) and [Appendix 18.1](#).
- (E) See [Section 7.0](#)

(F) To be ordered the same day (or within 7 days) if hepatitis flare occurs.

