11.0 STATISTICAL CONSIDERATIONS

11.1 Primary Endpoint

The following design pertains to each of the different study cohorts (chronic HBV [Cohort 1] and past HBV [Cohort 2]).

The primary endpoint for the clinical study is the time until adverse liver outcome. Patients will be assessed every 4 weeks (+/- 2 weeks) for the first 24 weeks, then every 8 weeks until 24 months. The study will recruit patients with multiple different cancer types, but predominantly lung, breast, colon, prostate, gynecological, and head and neck cancers. Since patient prognosis is sufficiently poor to be receiving anti-cancer therapy, dropout due to non-liver related death will be a significant factor in the design. One-year overall survival is anticipated to be 80% for the combined cohort. Therefore, non-liver related death represents a competing risk in the detection of adverse liver outcomes, which is accounted for in the study design. Both time to first evidence of adverse liver event and non-liver related death are assumed to exhibit exponential decline.

The rate of adverse liver outcomes in this population is not well characterized, as most studies in the literature only report on rates of HBV reactivation or hepatitis flares. For design purposes, the best estimate of the researchers is that 10% of both chronic (Cohort 1) and past (Cohort 2) HBV patients will experience an adverse liver outcome within one

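### The last sentence of Section 7.8 ends scheduled assessments at a treatment-removal criterion, against the 24-month schedule stated elsewhere; followed literally, the lost liver-outcome ascertainment in Cohort 1 would fall mostly in Arm 1

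*Combined protocol and SAP*

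**What the plan says.** Section 7.8 opens with "All patients will be followed until death or 24 months after registration, whichever occurs first". Its last sentence then sets another end point: "Patients should continue to have their protocol-scheduled assessments until one of the outlined criteria for removal listed in" Section 7.6 is reached.

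The 7.6 list concerns removal from protocol treatment. Besides 24 months on study and withdrawal, it contains antiviral delay over 30 days, unacceptable antiviral toxicity, and "If receiving anti-viral treatment, completion of anti-viral treatment 6 months after discontinuing all anti-cancer therapy" (or 24 months after registration, if earlier). Only the withdrawal item says that site forms continue through Week 104.

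Other sections give a 24-month schedule that does not depend on treatment:

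- 7.4: "During anti-cancer therapy and for 24 months from initial registration, all patients will undergo monitoring for HBV reactivation and adverse liver outcomes".
- Calendar 9.1 has a column headed "Follow-Up after Off HBV Treatment (Every 8 Weeks Through Week 104"; calendars 9.2 and 9.3 carry the same heading, "Follow-Up after Off HBV Treatment (Every 8 Weeks Through Week 104 (24 months".
- 11.1: "Patients will be assessed every 4 weeks (+/- 2 weeks) for the first 24 weeks, then every 8 weeks until 24 months".
- 7.1b: "All laboratory assessments and specimen collections must be completed at protocol-specified timepoints". This gives no duration and conflicts only through its pointer to Section 9.

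**The concern.** The laboratory part of the primary endpoint in 10.1 (bilirubin and INR) is found through scheduled bilirubin and ALT, with INR triggered by them under 7.4. A rule that ends these visits at treatment removal ends that route to the endpoint.

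The rule would not act equally on the two Cohort 1 arms. Every Arm 1 patient is assigned an antiviral and can meet the completion criterion. An Arm 2 patient can meet it only after reactivating and starting treatment; 11.2 anticipates 20% reactivation on the standard arm. The Arm 1 time lost would also begin when the antiviral stops, the period in which Section 3.0 reports severe exacerbations and asks for close hepatic monitoring.

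At stake is equal ascertainment between Arms 1 and 2, and hence power. Validity is at stake only under further conditions. Cohort 2 cannot be sized, because the rate of antiviral use in Arm 4 is not given.

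**Working it through.** **Inputs from the documents.** Control liver-event rate 10% at one year (11.1), so λ0 = −ln 0.90 = 0.1054 per year; HR 0.30, so λ1 = 0.0316. Deaths 20% at one year, μ = 0.2231. Standard-arm reactivation 20% (11.2), read as a one-year hazard r = 0.2231. One-sided alpha 0.05, 100 evaluable patients per arm.

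**Assumptions not in the documents.** Last anti-cancer dose D = 3, 6 or 12 months after registration, so Arm 1 antivirals end at c = month 9, 12 or 18. Nothing is captured after c. The share of sites reading 7.8 literally is unknown and is varied.

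**Plan's own figure.** Cumulative incidence = λ/(λ+μ) × (1 − exp(−(λ+μ)T)). At T = 2 years this is 15.45% for control and 4.95% for HR 0.30, or 20.4 events per 200 patients. Freedman power = Φ(√20.4 × 0.7/1.3 − 1.645) = Φ(0.787) = 78.4%, close to the stated 80%. A simulated log-rank test gives about 82%. Fixed 24-month follow-up is an assumption, since 11.1 does not state the follow-up behind its power; at 12 months the formula gives only 58.0%.

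**Visits lost in Arm 1.** Sections 7.4 and 9 give 17 visits (weeks 0 to 24 every 4 weeks, then weeks 32 to 104 every 8). A literal stop at month 9, 12 or 18 drops 9, 7 or 4 of them. For D of 18 months or more nothing is lost.

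**Person-time lost.** Years at risk after c = (e^(−hc) − e^(−2h))/h, with h = λ+μ (0.2548 in Arm 1, 0.3285 in Arm 2). Totals over 24 months are 1.567 and 1.466 years per patient. In Arm 2 only patients who reactivate before c are counted: r/(r+μ) × (1 − exp(−(r+μ)c)).

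| Cut-off | Arm 1 years lost (share of total) | Arm 2 reactivated before c | Arm 2 years lost per randomised patient | Arm 1 share of lost time | Arm 1 share of missed events, HR 0.30 |
|---|---|---|---|---|---|
| Month 9 | 0.884 (56%) | 14.2% | 0.142 × 0.801 = 0.114 | 89% | 70% |
| Month 12 | 0.684 (44%) | 18.0% | 0.180 × 0.614 = 0.110 | 86% | 65% |
| Month 18 | 0.320 (20%) | 24.4% | 0.244 × 0.282 = 0.069 | 82% | 58% |

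The event share weights lost time by each arm's hazard; at month 9, 0.0316 × 0.884 = 0.0279 against 0.1054 × 0.114 = 0.0120. Using instead the fraction reactivated among patients still at risk, 1 − e^(−rc) = 15.4%, 20.0% or 28.4%, the time shares are 88%, 85% and 80% and the event shares 68%, 63% and 55%. The range is thus roughly 80-89% of lost time and 55-70% of missed events. Per 111 patients, Arm 1 would miss up to 3.1, 2.4 or 1.1 of 5.5 expected events.

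**Power if affected patients are censored at c** (simulated log-rank, HR 0.30):

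| Patients affected | Month 9 | Month 12 | Month 18 |
|---|---|---|---|
| None | 82% | 82% | 82% |
| A quarter | 78% | 79% | 81% |
| Half | 73% | 75% | 79% |
| All | 52% | 61% | 74% |

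These runs treated 30% of Arm 2. Other fractions, including the pre-cut-off ones above, move power by about 1 point. Type I error stayed near 5%. A formula that only counts total events gives a milder 73-77% for all sites literal, but it credits Arm 2 events that occur when no Arm 1 patient remains at risk, and those add nothing to a log-rank or Cox comparison.

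**The case against.** The strongest reply is that the literal reading is hard to sustain. Section 7.6 is about treatment, the calendars have a column for patients off HBV treatment, and a site reading 7.4 beside its calendar would continue. For HBsAg-positive patients, which means Cohort 1, 7.4 also recommends specialist contact after study treatment ends so that monitoring goes on. Appendix 18.1c has ALT, bilirubin and INR recorded at the Section 9 time points, and 14.4f and 14.4g still require reports of recognised liver outcomes and deaths. Site uptake and therapy duration are unknown, and with a quarter of patients affected the power cost is only about 1 to 4 points.

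Most of this stands. It makes a large loss unlikely, and the power figures above are worst cases. It does not remove the contradiction: the sentence sits in the follow-up section, carries no on-treatment limit, and refers to a list that mixes study-end and treatment-end reasons.

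A reader might infer that the plan itself truncates Arm 1 follow-up, or that it inflates type I error in favour of prophylaxis. The documents do not support either. Every other section sets 24 months, and 11.1 censors non-death dropouts. Bias toward prophylaxis needs informative censoring, for example a rise in risk after the antiviral stops, or patients carried as event-free. Under the latter, with a quarter affected and 30% of Arm 2 treated, simulated type I error was between 0.05 and 0.10, but 11.1 does not describe that handling.

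One caution on 9.2: in this copy its bilirubin and ALT rows show one mark fewer than in 9.1 and 9.3. That may be a layout artefact, and nothing here rests on it.

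**Conclusion.** The last sentence of 7.8 is wrong as written. It contradicts its own section's first sentence, 7.4, calendars 9.1 to 9.3 and 11.1. An on-treatment meaning is the likely intent, but the text does not give it. Where followed literally, lost ascertainment in Cohort 1 falls mostly in Arm 1: about 80-89% of lost time and 55-70% of missed events under HR 0.30. With non-informative censoring the cost is power rather than type I error, ranging from negligible to the all-sites-literal worst case. The size rests on assumed therapy duration, assumed uptake and no capture after the cut-off. Section 11.1 does not say whether a patient whose assessments stop under 7.6 counts as a censored dropout. This should be fixed because the remedy is small, not because a large loss is expected.

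**What to change.** Reconcile the last sentence of 7.8 with 7.4, 9.1 to 9.3 and 11.1: meeting a 7.6 criterion does not end the liver-outcome assessments already scheduled through Week 104 in any arm, except on death or withdrawal of consent. Add to 11.1 that patients whose assessments nevertheless stop early are censored at their last assessment, and that their number is reported by arm. The cost is one sentence in each section; the visits are already in the schedule.

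Two nearby mismatches need reconciling separately and add no weight to this point. The Arm 2 and Arm 3 tables treat 6 months after anti-cancer therapy as an upper limit, while the accompanying text and 10.2c treat it as a lower one, and 7.6 has completion at 6 months. Footnote C in 7.2 points to 8.2 for cessation details that 8.2 does not give. No view is taken here on which wording is right.
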